6.3.1 INTERVENTIONIST TRAINING AND ACCOUNTABILITY

Two interventionists will deliver both SPIRIT modalities. Interventionist minimal qualification is having at least 2 years of clinical experience in caring for people with AD as a nurse (RN or APRN) or social worker. Interventionist training (led by Drs. [name] and [name]) will consist of a 3½-day competency-based program used in our previous trials using training manuals. Module 1 (1 day) focuses on understanding AD and end-of-life care issues, communication as key to improving end-of-life care, and the Representational Approach (theoretical underpinnings of SPIRIT); Module 2 (1 day) is a skill-based session on delivery of the SPIRIT intervention (e.g., communication behaviors and enhanced consent techniques), including role plays; Module 3 (1/2 day) focuses on videoconferencing procedures and etiquette, features of Zoom, and handling technical problems (adapted from the Tele-Savvy Training manual). A 2-week practice period is then scheduled for integration of skills. Module 4 (1 day) involves skill-demonstration and certification.

6.3.2 FORMULATION, APPEARANCE, PACKAGING, AND LABELING

Not applicable.

6.3.3 PRODUCT STORAGE AND STABILITY

Not applicable.

6.3.4 PREPARATION

Not applicable.

6.4 STUDY INTERVENTION COMPLIANCE

To promote consistency and quality of intervention delivery, the SPIRIT Interview Guide will be used during each session. To monitor fidelity, we will use two data sources. 1) The SPIRIT Interview Guide will direct the interventionist to document performance data after each patient-surrogate dyad encounter; these data will be entered into the Research Electronic Data Capture [REDCap] by the project director. The Guide has a checklist of SPIRIT components, including start and finish times, and brief self-evaluation. 2) As in our previous studies, all intervention sessions will be audio-recorded. Every 2 months, 50% of sessions randomly selected from SPIRIT-remote will be reviewed by the PI (approximately 2 sessions from each group). Using the modified Treatment Fidelity Assessment Tool, the interventionist's adherence to intervention content, process, and duration will be evaluated on a 3-point scale (1=appropriate, 3=skipped). Problems detected including drift from protocol will be discussed with the interventionist and re-training will be provided if adherence is <80% based on the Fidelity Assessment Tool.

6.5 CONCOMITANT THERAPY

Not applicable (all patients receive usual care related to advance care planning). Patient participants will receive usual care only or usual care plus an intervention condition.

6.5.1 RESCUE MEDICINE

Not applicable.

7 STUDY INTERVENTION DISCONTINUATION AND PARTICIPANT DISCONTINUATION/WITHDRAWAL

7.1 DISCONTINUATION OF STUDY INTERVENTION

SPIRIT is a one-time intervention. Any incomplete intervention will be tracked along with the reason.

7.2 PARTICIPANT DISCONTINUATION/WITHDRAWAL FROM THE STUDY

Participants are free to withdraw from participation in the study at any time upon request.

An investigator may discontinue or withdraw a participant from the study for the following reasons:

- If the participant meets an exclusion criterion that precludes further study participation.

The reason for participant discontinuation or withdrawal from the study will be recorded on the study REDCap. Subjects from the clinic randomized to initial SPIRIT who sign the informed consent form but do not receive the study intervention may be replaced. Subjects in the initial SPIRIT who sign the informed consent form and receive the study intervention, and subsequently withdraw from the study will not be replaced.

7.3 LOST TO FOLLOW-UP

A patient or surrogate participant will be considered lost to follow-up if he or she fails to complete the scheduled post-intervention follow-up (for studies in both Stages) and is unable to be contacted by the study site staff until the end of the 12-month follow-up period (for Stage 1B study). Or, a surrogate participant who has been selected for a semi-structured interview will be considered lost to follow-up if he or she fails to complete the scheduled 12-month follow-up and is unable to be contacted by the study site staff.

The following actions must be taken if a participant is determined to be lost to follow-up:

- The research staff will attempt to contact the participant and reschedule the missed appointment for 4 weeks and ascertain if the participant wishes to continue in the study.
- Before a participant is deemed lost to follow-up, the investigator or designee will make every effort to regain contact with the participant (where possible, 3 telephone calls and, if necessary, a certified letter to the participant's last known mailing address or local equivalent methods). These contact attempts will be documented in the participant's record in REDCap.
- Should the participant continue to be unreachable, he or she will be considered to have withdrawn from the study with a primary reason of lost to follow-up.

8 STUDY ASSESSMENTS AND PROCEDURES

8.1 OUTCOME ASSESSMENTS

In Stage 1A,

Feasibility of recruiting and retaining patients with mild AD and surrogates for SPIRIT-in person and SPIRIT-remote will be assessed by tracking the numbers of dyads who are eligible and who agree to participate, and the reasons for refusal and withdrawals. Feasibility of conducting SPIRIT-in person and SPIRIT-remote will be assessed by tracking the number of dyads who complete their session, the number of incomplete or interrupted sessions, and

the minutes required to complete SPIRIT-in person and SPIRIT-remote. We will also explore whether these variables are associated with patients' MoCA or MMSE scores.

Acceptability. After the outcome assessment, the research assistant will conduct a brief semi-structured interview (10-15 minutes) with each member of the dyad to ask about: the overall experience with SPIRIT; any facets of the intervention that the participant found helpful/not helpful and the reasons; pacing, length, and modality; and suggestions for improvement. This interview will be audio-recorded and transcribed for analysis.

Outcomes

Preparedness for end-of-life decision making (measured at baseline and 2-3 days after the intervention or randomization) Note flexibility may be necessary due to challenges of the population and demands of scheduling both patients and surrogates:

- **Dyad congruence** will be assessed using the Goals-of-Care Tool,^{28,30} which has been modified to include two scenarios relevant to the context of AD. In the first, the patient has progressed to advanced dementia and develops a severe infection and is admitted to a hospital; the medical team believes recovery unlikely and continuing life-sustaining treatment would no longer be beneficial. There are three response options: "The goals of care should focus on delaying my death no matter what, and thus I want to continue life-sustaining treatment", "The goals of care should focus on my comfort and peace, and thus I do not want life-sustaining treatment", and "I am not sure". In the second scenario, the patient has progressed to advanced dementia and develops a severe infection. The nursing home staff is asking whether the patient should be taken to an ED, which will lead to hospitalization with life-sustaining treatments. Patients and surrogates complete this tool independently and their responses are then compared to determine dyad congruence -- either congruent in both scenarios or incongruent. If both members of the dyad endorse "I am not sure", they are considered incongruent.
- **Patient decisional conflict** will be measured using the 13-item Decisional Conflict Scale (DCS), a validated measure in the context of end-of-life decision making²⁷; higher scores indicate greater difficulty in weighing benefits and burdens of life-sustaining treatments and decision making (range 1-5; Cronbach's $\alpha = 0.8 - .93$ ^{27,28,30,121}).
- **Surrogate decision-making confidence** will be measured using the 5-item Decision Making Confidence (DMC) scale (Cronbach's $\alpha = 0.81-0.90$ ^{28,58}); higher scores reflect greater comfort in performing as a surrogate (0="not confident at all" to 4="very confident"). DMC assesses a surrogate's confidence in: knowing the patient's wishes, ability to make treatment decisions even in a highly stressful situation, ability to seek information about risks and benefits of medical choices, ability to handle unwanted pressure from others, and ability to communicate with providers about the patient's wishes.
- We will also assess the **overall preparedness for end-of-life decision making** using the 26-item investigator-developed measure. The measure assesses the level of preparedness for end-of-life decision making in the cognitive, emotional, and behavioral dimensions on a 4-point scale (4=strongly agree to 1=strongly disagree) with higher scores indicating higher levels of preparedness. Patient and surrogate each will complete this measure separately.

In Stage 1B,

Acceptability. Patient and surrogate acceptability will be assessed using the 10-item ACP Acceptability Questionnaire developed from our previous trial.²⁴ Participants are asked how strongly they agree or disagree (4 to 1) with statements about their experience with SPIRIT sessions, including duration, interactions with the interventionist, level of comfort and satisfaction. Higher scores indicate greater acceptability. Each patient and surrogate will complete this survey following the preparedness outcome measures after the intervention.

Preparedness for end-of-life decision making (measured at baseline and ideally 2-3 days after the intervention or randomization):

- **Dyad congruence** will be assessed using the Goals-of-Care Tool,^{28,30} which has been modified to include two scenarios relevant to the context of AD. In the first, the patient has progressed to advanced dementia and develops a severe infection and is admitted to a hospital; the medical team believes recovery unlikely and continuing life-sustaining treatment would no longer be beneficial. There are three response options: “The goals of care should focus on delaying my death no matter what, and thus I want to continue life-sustaining treatment”, “The goals of care should focus on my comfort and peace, and thus I do not want life-sustaining treatment”, and “I am not sure”. In the second scenario, the patient has progressed to advanced dementia and develops a severe infection. The nursing home staff is asking whether the patient should be taken to an ED, which will lead to hospitalization with life-sustaining treatments. Patients and surrogates complete this tool independently and their responses are then compared to determine dyad congruence -- either congruent in both scenarios or incongruent. If both members of the dyad endorse “I am not sure”, they are considered incongruent.
- **Surrogate decision-making confidence** will be measured using the 5-item Decision Making Confidence (DMC) scale (Cronbach’s $\alpha = 0.81-0.90$ ^{28,58}); higher scores reflect greater comfort in performing as a surrogate (0=“not confident at all” to 4=“very confident”). DMC assesses a surrogate’s confidence in: knowing the patient’s wishes, ability to make treatment decisions even in a highly stressful situation, ability to seek information about risks and benefits of medical choices, ability to handle unwanted pressure from others, and ability to communicate with providers about the patient’s wishes.
- We will also assess the **overall preparedness for end-of-life decision making** using the investigator-developed measure. The measure assesses the level of preparedness for end-of-life decision making in the cognitive, emotional, and behavioral dimensions on a 4-point scale (4=strongly agree to 1=strongly disagree) with higher scores indicating higher levels of preparedness. Patient and surrogate each will complete this measure separately.

Completion of Advance Directives (at 12 months). A research assistant will review the patient’s medical record to determine if the patient has completed an advance directive (a medical power of attorney or living will) by 12 months. If there is no documentation, the research assistant will call the surrogate to confirm.

Surrogates’ Perceived Impact of SPIRIT (intervention group only). At 12 months, 44-46 surrogates will participate in a semi-structured interview by phone: approximately 26 surrogates of patients who have progressed to an advanced stage (CDR score > 1 ; 22% progression rate^{33,113-115}) and 20% randomly selected surrogates of patients who have not progressed (~18-20 surrogates). A research assistant will review medical records to identify if a patient’s dementia has progressed. A trained interviewer/research assistant will conduct the interview using the Perceived Impact Interview Guide, which includes questions about surrogates’ experiences with the treatment condition, the perceived impact of the treatment condition on their loved ones and themselves, and what they found most and least helpful and why. This 15-30 minute interview will be audio-recorded and transcribed.

Descriptors and Potential Covariates (collected at baseline). Patients and surrogates will each complete a Sociodemographic Profile which includes demographic information and previous end-of-life decision-making experience. Patients’ clinical characteristics, (date of dementia diagnosis, CDR score, MoCA or MMSE scores, and comorbid conditions) will be abstracted from the patient’s medical records. For patients whom we do not have access to their medical records, study staff will gather a patient’s clinical characteristics from the surrogate. The Medical Profile at Enrollment and the Quarterly Medical Record Review will both require surrogate report when medical records are unavailable.

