The most challenging aspects of designing this intervention trial are: a) determining an optimal follow-up time point and data collection mode to minimize the potential influence of patients' cognitive impairment on the outcome assessment, and b) maintaining blinding of data collectors. The first follow-up time point (Ideally 2-3 days post intervention however, consideration is given to difficulty of scheduling dyads and extension may result is to evaluate the impact of SPIRIT on preparedness outcomes while minimizing the potential influence of the patient's impaired ability to recall what was discussed during the SPIRIT session (i.e., the patient needs to recall what he/she clarified as goals-of-care preferences). We considered measuring the outcomes immediately following the intervention, but this would preclude blinding the data collector because of the modality difference. The second follow-up time (12 months post intervention) was chosen to help maximize the number of patients whose conditions progress to an advanced stage within the study period so that we can explore how surrogates experience having or not having an in-depth ACP discussion before the window of opportunity has closed. Although not ideal for people with mild AD, telephone-based data collection was chosen to assure blinding of data collectors and to reduce participants' travel burden. We have used phone-based data collection extensively in our previous studies with seriously ill patients and their surrogates using the procedures described above (see Post-Intervention Assessment).

As in our previous studies, we chose usual care as a comparison condition rather than an attention placebo control. In addition to the fact that there is no methodological standard for attention placebo controls in trials of psychosocial interventions,¹¹⁶ in the context of preparing for future medical care and end-of-life decision making, an attention placebo (information and discussion irrelevant to the context) would not meet the participants' expectations or motivation to participate in the study, and could cause a high refusal rate, dissatisfaction, and disproportional dropouts.¹¹⁶ We will offer SPIRIT-remote to control dyads at the completion of the 1 year follow-up if the patient has not progressed to moderate AD. The same protocol was used in our previous efficacy trial with 12-month follow-ups, and a wait-list control did not result in disproportional dropouts (SPIRIT [5.5%] vs usual care [2.0%]).³⁰

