If a dyad is assigned to the SPIRIT-remote group, a research assistant trained to handle technical aspects of Zoom will schedule a phone call to take the surrogate through the steps of using email to follow URL links that open Zoom. He/she will also guide the surrogate through practice in using basic videoconference operations, e.g., accepting an incoming conference invitation, viewing shared documents, muting/unmuting the microphone or camera, and ending the call. For dyads with a computer without video capabilities, a loaner web cam (and headset and microphone as needed) will be shipped as soon as the group assignment is known. This research assistant will initiate the Zoom call for SPIRIT-remote sessions and silently observe sessions to troubleshoot difficulties the dyad or interventionist might encounter. These procedures have been used effectively in the Tele-Savvy pilot and current R01 project. The interventionist will confirm a follow-up call for outcome assessment to occur in the next 2-3 days ideally.

Usual Care at the Emory ADC. At the time of the diagnosis of a dementing illness, an advanced practice nurse provides written information on advance directives to a patient and his/her family caregiver and reviews this information and encourages them to complete an advanced directive. This typically takes about 10 minutes. Patients and their family members may be referred to attorneys who can assist them in completing an advance directive. If completed, the presence of an advanced directive is documented in the electronic medical record and a copy of the advance directive is scanned to the electronic chart. Patients and families may be referred to a support group program organized by a social worker in which legal and financial issues are discussed in a group setting (by a lawyer). We will review the patient’s medical records at the clinic at baseline and quarterly to track activities associated with usual care. To capture any changes in usual care, policy and procedures related to ACP at the clinic will be reviewed every 6 months by a research assistant.

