6.2 PREPARATION/HANDLING/STORAGE/ACCOUNTABILITY

6.3 MEASURES TO MINIMIZE BIAS: RANDOMIZATION AND BLINDING

For Stage 1B pilot testing, [name] (statistician/Co-I) will generate a randomization scheme using stratified (by race, white vs non-white study site, Emory vs Grady), permuted block randomization with block size 6, using a random-number generator. Dyads will be randomized with equal allocation (1:1:1) to SPIRIT-in person, SPIRIT-remote, or usual care.

With Revision 14, randomization will be stratified by race (white vs non-white) within recruitment site (Emory, Rush, and Northwestern), with equal allocation to SPIRIT-in person or usual care.

Due to the nature of the intervention, blinding dyads to their group allocation is impossible, but the research staff assessing outcomes will be blind. Immediately after the completion of the baseline assessment by phone, the data collector will open a sealed envelope to identify group assignment and schedule an intervention session to take place ~2 weeks hence for SPIRIT- in person or –remote (with revision 14, all SPIRIT-remote), as well as a follow-up data collection session in the next 2-3 days.

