8.3.5 ADVERSE EVENT REPORTING

The possible adverse reactions, such as emotional distress during the intervention session, if ever occurs, will be tracked (documented in the study REDCap) and the aggregated numbers will be reported at the upcoming biannual DSMC meeting.

Between the post-intervention (or post-randomization for the usual care group) follow-up and the 12-month follow-up with selected surrogates, there will be no study procedures that are required for participants other than our monthly check-in calls and there will be no data collection involved. Thus, the study team will have no way of knowing if there are any disease-related events (DREs) in the study population. **However, any participant's death, if known, will be reported to IRB through annual progress report and included in the NIH annual progress report.**

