9.4.2 ANALYSIS OF THE PRIMARY ENDPOINT(S)

SPIRIT effects on the preparedness outcomes: For dyad congruence, a binary outcome (congruent or not congruent), a generalized mixed effects logistic regression model will be used. Specifically, a random intercept model will be used to account for dyad level variation over time while treatment group, time (baseline and post-intervention), and treatment x time interaction will be treated as fixed effects. If there is a significant treatment x time interaction ($\alpha<0.05$) (an overall treatment effect), then two contrasts will be tested for individual treatment effectiveness (usual care vs SPIRIT-in person and usual care vs SPIRIT-remote). Adjustments for multiple pairwise comparisons will be made using Tukey's test. Surrogate DMC and preparedness scores, we will use linear mixed

effects regression models, adjusting for potential covariates as appropriate. Since this is not a non-inferiority trial where two or more interventions that have been proven to be superior to usual care are being compared, the contrast, SPIRIT-in person vs SPIRIT-remote, cannot be tested. However, if superiority of the two modalities to usual care is determined, the estimated group differences could be used for selecting a non-inferiority margin or equivalence range^{124,125} for future studies.

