In light of the changes in study design (V12), we will update the statistical analysis plan. In particular, the preparedness outcomes from the 2-arm and 3-arm RCTs will be analyzed individually to evaluate the effect of the interventions. We will use mixed effects models as mentioned above and use contrasts to compare between the three and two intervention groups respectively. In addition to separate analyses, we will conduct pooled analysis by using analysis of variance methods (ANOVA) and incorporating an indicator variable for study and evaluate the (study x intervention group) interaction effect. We will also explore a meta-analysis approach to obtain a common intervention effect of SPIRIT-remote vs usual-care, from the two studies. If the effect sizes obtained from the individual studies are relatively homogeneous, their individual results may be combined to produce an estimate of the intervention effect. A weighted pooled estimate of effect size can be obtained, using the inverse of each study's variance as the weight. Because the studies are almost identical, we anticipate the variance to be fairly similar in both cases; a fixed effects approach will be used to estimate the variance.

With revision V14: The revised statistical analysis plan will be similar to that described in V12. Our primary aim will be to evaluate the effect of the SPIRIT- remote intervention group versus usual care on the outcomes of interest. We will use generalized linear mixed effect modeling and compare changes in treatment group means or proportions over time using contrasts. Because we only have 3 clusters (sites), fitting a multilevel model would not be feasible. We will instead adjust for site as a fixed effect in our mixed effects model. We will also compare our findings to those from Stage 1A to assess any substantial difference in effect sizes.

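### As written, usual-care dyads appear to be reassessed about 2-3 days after randomization and SPIRIT dyads about 16-17 days after it, so elapsed time is aligned with arm in the primary contrast

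*Combined protocol and SAP*

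**What the plan says.** Four places in the combined protocol and SAP set the timing of the first Stage 1B follow-up.

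- **Section 6.3** opens the allocation envelope "Immediately after the completion of the baseline assessment by phone". The data collector then has to "schedule an intervention session to take place ~2 weeks hence". Days from randomization and days from baseline are therefore the same.
- **Section 6.1.1**, on SPIRIT-remote: "The interventionist will confirm a follow-up call for outcome assessment to occur in the next 2-3 days ideally".
- **Section 8.1 (Stage 1B)** says the preparedness outcomes are "measured at baseline and ideally 2-3 days after the intervention or randomization".
- **Section 8.3.5** shows which arm the second anchor belongs to: "Between the post-intervention (or post-randomization for the usual care group) follow-up and the 12-month follow-up".

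Section 9.4.2 models the outcomes with treatment group, "time (baseline and post-intervention), and treatment x time interaction will be treated as fixed effects". The V14 text will "compare changes in treatment group means or proportions over time using contrasts" and adds site as a fixed effect. Actual days since baseline do not appear in the model or in the covariate list in section 8.1.

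**The concern.** Usual-care dyads have no session before this assessment, so randomization is the only anchor in section 8.1 that fits them. Followed literally, the control call comes 2-3 days after baseline, while the SPIRIT call comes about two weeks later than that. The two-level time factor treats both calls as the same post-intervention visit.

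The treatment-by-time contrast then contains the effect of SPIRIT plus whatever changes over the additional fortnight in any dyad. Both members answer the goals-of-care questions at baseline. After 2-3 days they may still remember and repeat their answers. After 16-17 days they may have forgotten them, talked the questions over because the questionnaire raised them, or simply shifted. Talk prompted by learning the assignment is different: it belongs to the intent-to-treat effect (section 9.3) and is not counted as bias here.

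The protocol itself treats the timing of this visit as delicate. Section 4.2 chooses it because of the patient's "impaired ability to recall what was discussed during the SPIRIT session". All three primary outcomes share the exposure. It matters for estimation as well as testing: for surrogate confidence, section 9.2 makes estimation of population parameters the aim, and an elapsed-time bias goes straight into that estimate.

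**Working it through.** **Target days, from the documents.** Day 0 is baseline and randomization.

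- SPIRIT: 14 + 2 to 14 + 3 = day 16-17.
- Usual care, on the randomization anchor: day 2-3.
- Gap: 16 - 3 = 13 to 17 - 2 = 15 days; at midpoints, 16.5 - 2.5 = 14 days, or 2 weeks.
- Ratio of intervals: 16/3 = 5.3 to 17/2 = 8.5.
- The two-week delay is approximate. With equal 2-3 day offsets the gap equals the delay to the session, so an assumed delay of 10-18 days gives a gap of 10-18 days.

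**Can the analysis recover this?** If the targets are met, the intervals do not overlap between arms, so days since baseline is nearly a copy of the arm indicator. Rescheduling for up to 4 weeks (section 7.3) could create some overlap, but only by accident and through dyads who are hard to reach.

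**Size, as an illustration.** The documents give no drift rate, control congruence rate or within-dyad correlation, so all three are assumed. There is no true treatment effect, and weekly drift is the same in both arms.

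*Congruence.* Follow-up rate = base + weekly drift × days/7, with 2.5 days for usual care and 16.5 for SPIRIT. At base 40%:

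- +5 points/week: 41.8% v 51.8%, OR = (0.518/0.482)/(0.418/0.582) = 1.50.
- -5 points/week: 38.2% v 28.2%, OR = 0.64.
- +2.5 and -2.5 points/week: OR = 1.23 and 0.81.

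Over base rates of 30-60%, 2.5 points/week gives 1.22-1.25 (or 0.77-0.82), and 5 points/week gives 1.50-1.57 (or 0.57-0.67).

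The chance of a significant interaction at 0.05 was simulated under the planned random-intercept logistic model. Settings: 1,000 trials per cell, base 40%, site term omitted, random-intercept SD 1.55, 2.70 or 4.91 (within-dyad correlation about 0.3, 0.5 or 0.7), likelihood-ratio test, Monte Carlo error at most 1.5 points. The arm sizes are 120/2 = 60 and 72/2 = 36.

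| Drift (points/week) | 60 per arm, corr. 0.3 / 0.5 / 0.7 | 36 per arm, corr. 0.3 / 0.5 / 0.7 |
|---|---|---|
| 0 | .057 / .055 / .049 | .059 / .068 / .062 |
| +2.5 | .088 / .084 / .118 | .068 / .071 / .108 |
| -2.5 | .080 / .083 / .126 | .060 / .082 / .100 |
| +5 | .160 / .185 / .285 | .119 / .130 / .189 |
| -5 | .198 / .218 / .319 | .127 / .157 / .212 |

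A simple two-proportion comparison at follow-up, 60 per arm, is of the same order: a 5-point difference gives about 9% rejection and a 10-point difference 20-21%.

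*Surrogate scales.* Bias = weekly drift × 2 weeks, so 0.01, 0.05 and 0.10 SD/week give 0.02, 0.10 and 0.20 SD. The first equals the short-term d = .02 in section 9.2. With SE = sqrt(2(1 - rho)) × sqrt(2/n), the noncentral-t rejection rates for rho 0.3 / 0.5 / 0.7 are:

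| Bias | 60 per arm | 36 per arm |
|---|---|---|
| 0.10 SD | .074 / .084 / .108 | .064 / .070 / .084 |
| 0.20 SD | .151 / .192 / .289 | .109 / .133 / .191 |

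**The case against.** The usual-care day is inferred. No sentence states it, and the schemas, where per-arm time points would normally appear, are not shown. The pairing of intervention and randomization also occurs in the Stage 1A part of section 8.1, where it has no evident use because section 6.3 describes randomization only for Stage 1B. It may be carried-over text. Section 8.3.5 gives an anchor but no interval, and a call on day 16 is also post-randomization. The synopsis and section 3 place the comparison 2-3 days after the intervention, and section 4.2 speaks of one first follow-up point. The last clause of section 6.3 does not say from which event its 2-3 days run. The drift sizes are assumptions, and little advance care planning would be expected from usual care within two weeks when visits are typically six months apart (section 4.2).

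These points limit certainty about what the sponsor intends, and they mean that neither the presence nor the direction of bias is shown. They do not supply a matched interval. If matching was intended, no readable passage says so, and staff following section 8.1 would call controls early. Sparse usual-care activity does not remove retest or recall effects. The wording needs correction on either reading.

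**Conclusion.** The concern holds, with medium confidence, and should be fixed. Read in the most natural way, the plan assesses usual care at about day 2-3 and SPIRIT at about day 16-17, a gap of 13-15 days that the two-level time term and the site adjustment leave untouched. This rests on taking randomization as the usual-care anchor with the 2-3 day interval attached to it.

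Only the gap comes from the documents. The bias figures depend on assumed drift, and the upper rejection rates (about 16-32% at 60 per arm) need 5 points per week. Drift of that order could not produce the planning odds ratio of 4.3. The exposure matters more for small effects and for the effect-size estimates that this pilot is meant to deliver.

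**What to change.** - Keep the SPIRIT call 2-3 days after the session, as the recall rationale in section 4.2 requires.
- Schedule the Stage 1B usual-care call at the matching interval from randomization, about two weeks plus 2-3 days, with the same window.
- Assess SPIRIT dyads who receive no session at that same target day.
- Reword section 8.1 to give the target day for each arm, and bring sections 6.3 and 8.3.5 into line with it.
- Record the actual days from baseline to follow-up and report them by arm.

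The cost is protocol wording and a later control call, with possibly slightly more usual-care drop-out before the primary assessment. The sample size does not change. If some controls have already been called early, the usual-care arm will contain two intervals; the report of actual days will show how many dyads are affected.
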